3. GLOSSARY OF ABBREVIATIONS

AE	Adverse event
ATMP	Advanced Therapy Medicinal Product
BM	Bone marrow
CMV	Cytomegalovirus
CNS	Central nervous system
CRF	Case report form
CRO	Clinical Research Organisation
CSF	Cerebrospinal fluid
ECG	Electrocardiogram
e-CRF	Electronic case report form
EDSS	Extended Disability Status Scale
FS	Functional systems
FSS	Functional subscores
GA	Glatiramer acetate
GCP	Good Clinical Practice
GEL	Gadolinium enhancing lesion
GP	General Practitioner
HIV	Human Immunodeficiency Virus
HTLV	Human T-cell Lymphotropic Virus
ICH-GCP	International Conference on Harmonisation on Good Clinical Practice
IFN-β	Interferon β
iPSP	Induced pluripotent stem cells
IV	Intravenous
LP	Lumbar puncture
MHRA	Medicines and Healthcare Regulatory Agency
MRI	Magnetic resonance imaging
MS	Multiple sclerosis
MSC	Mesenchymal Stem/Stromal Cells
MSFC	Multiple Sclerosis Functional Composite
MSIS-29	Multiple Sclerosis Impact Scale-29
NB	Negative binomial
NHS	National Health Service
PASAT	Paced Auditory Serial Addition Test
PBMC	Peripheral blood mononuclear cell
PIS	Patient Information Sheet
PPMS	Primary progressive multiple sclerosis
R&D	Research and Development
RRMS	Relapsing remitting multiple sclerosis
SAE	Serious adverse event
SF-36	Short Form-36
SOP	Standard Operating Procedure
SPMS	Secondary progressive multiple sclerosis
SSA	Site Specific Assessment
SUSAR	Suspected unexpected serious adverse reaction
T25-FW	Timed 25-Foot Walk

KEYWORDS: Multiple Sclerosis, rapidly evolving, mesenchymal stem cells, bone marrow

4. STUDY SUMMARY

TITLE	Stem cells in Rapidly Evolving Active Multiple Sclerosis (STREAMS)
DESIGN	Randomised double-blind crossover study
AIMS	To describe the safety and efficacy of intravenously administered autologous MSCs in patients with Multiple sclerosis (MS).
OUTCOME MEASURES	
Primary outcome: To assess the safety of intravenous therapy with autologous MSCs in MS patients. The safety of MSCs infusion will be evaluated including frequency, timing and severity of any adverse events in both MSCs and placebo treatment groups. A statistical comparison of the number of adverse events between treatment groups will be carried out using a chi-square test.Co-Primary outcome: To assess the activity of autologous MSCs in MS patients. The total number of gadolinium-enhancing lesions (GEL) at MRI at weeks 4, 12 and 24 will be compared between treatment groups using a Negative Binomial (NB) regression analysis, adjusting for the number of GEL at baseline.Secondary outcomes: To gather preliminary information about the efficacy of the experimental treatment in terms of combined MRI activity, incidence of relapses and disability progression.
INCLUSION CRITERIA	
Patients with clinically and radiologically active multiple sclerosis as defined by:
 
1. Diagnosis of MS:
a. Relapsing remitting MS (RRMS): ≥ 1 moderate-severe relapse and ≥ 1 GEL in past 18 months or ≥ 1 moderate-severe relapse and ≥ 1 new T2 lesion in past 18 months.b. Secondary progressive MS (SPMS) with an increase of ≥ 1 EDSS point (if baseline EDSS ≤ 5.0) or 0.5 EDSS point (if baseline EDSS ≥ 5.5), in the previous 18 months and ≥ 1 GEL in past 18 months or ≥ 1 moderate-severe relapse and ≥ 1 new T2 lesion in past 18 months.c. Primary progressive MS (PPMS) patients with positive oligoclonal bands in the cerebrospinal fluid (CSF) and an increase of ≥ 1 EDSS point (if baseline EDSS ≤ 5.0) or 0.5 EDSS point (if baseline EDSS ≥ 5.5), or quantifiable, objective evidence of equivalent progression in the previous 18 months and ≥ 1 GEL in past 18 months or ≥ 1 new T2 lesion in past 18 months.2. Age 18 to 50 years.3. Disease duration 0 to 10 years from diagnosis (inclusive).4. EDSS 2.0 to 6.5 at screening evaluation.5. ≥ 1 GEL on MRI within 6 months prior to harvesting.6. Adequate culture of subject's MSCs and their release for clinical use.
TREATMENT	At week 0 and at week 24 a single infusion of either ex-vivo expanded autologous MSCs or suspension media will be administered intravenously. MSCs will be given at $1-2 \times 10^6$ MSC/Kg recipient body weight as at baseline.
DURATION	4-year project with staggered recruitment of subjects.

5. INTRODUCTION

5.1 BACKGROUND

5.1.1 The burden of MS

Multiple sclerosis (MS) is an inflammatory demyelinating disease associated with neurological impairment and affects approximately 100,000 young adults in the UK alone. MS can cause severe neurological impairment and affects the quality of life of both the individual and their families. MS is also a major socio-economic burden for society; it costs the United Kingdom approximately £12,000 per patient per year in the early stages of the disease but this rises to nearly £60,000/year in the advanced stages [1].

5.1.2. The challenges of MS

Multiple sclerosis (MS) is a very complex disorder both clinically and pathologically [2]. It is a chronic inflammatory disease of the central nervous system (CNS), which ultimately leads to myelin damage and axonal loss. The cause is unknown. Aetiology is multifactorial, but the key pathogenic event appears to be an uncontrolled response of components of the immune system (T and B lymphocytes) to myelin proteins.

There are different forms of the disease. About 80% of the patients have a relapsing-remitting (RR) course that, in two-thirds of cases, will evolve into a secondary progressive (SP) course after about 10-15 years of the disease. About 20% of the patients have a progressive course from onset, called "primary progressive MS" (PPMS) [3]. It is believed that, in MS, inflammation and irreversible neurodegeneration coexist, with inflammation causing relapses and neurodegeneration being responsible for the irreversible disability that characterises most patients with chronic disease. Clinical severity of MS ranges from benign disease, in which the patient remains fully functional in all neurological systems (15 years after disease onset) to malignant MS which is characterised by an aggressive course resulting in accumulation of severe disability or death within a short time. The majority of patients suffer from a disease course of intermediate severity between these two extremes.

5.1.3. Current treatments for MS

No curative therapies exist for MS. As both the aetiology and pathogenesis underlying the disease are, as yet, unknown and due to the existing clinical heterogeneity in the MS population, treatments are suboptimal and have been challenging to develop.

Current immunomodulatory therapies for MS - including the use of interferon β (IFN- β), glatiramer acetate (GA) or mitoxantrone - are only partially effective, do not abolish inflammation and have only modest effects on disease progression. Natalizumab, a humanised antibody against the cellular adhesion molecule (α -4 integrin), prevents the adhesion of lymphocytes and monocytes to endothelial cells of the blood brain barrier and therefore interferes with the entry of inflammatory cells into the CNS. It is more efficacious than the aforementioned immunomodulatory drugs, reducing the relapse rate by 68% and progression of disability by 54% when compared to placebo. There is a 1:1000 risk of developing progressive multifocal leukoencephalopathy (PML), an opportunistic infection of the CNS, in MS patients who have been treated with natalizumab for more than 2 years [4].

5.1.4. Development of new disease modifying treatments for MS

Recently, there have been significant developments in new treatment strategies for MS, including monoclonal antibodies for targeted immunomodulation (daclizumab, campath-1H, rituximab), limiting immune cell trafficking (e.g. fingolimod), or 'resetting' the immune system (through high-dose cyclophosphamide or haematopoietic stem cell transplantation) [5]. These therapies,

however, are at different stages of clinical development and evaluation of their safety and efficacy in treating MS requires further investigation.

5.1.5. Surrogate markers of disease in MS

Increasing evidence suggests that Magnetic Resonance Imaging (MRI) measures may offer sensitive, objective biomarkers of disease phenotype. MRI is the most widely utilised surrogate marker of disease activity in MS. Among MR metrics, the number of gadolinium-enhancing lesions (GEL) provides a measure of new inflammatory activity [6] and a large number of clinical trials have used gadolinium-enhanced lesions as the outcome measure. However, the relationship between such “conventional” MRI markers and the clinical evolution of disease is weak and MR metrics providing additional brain structural and metabolic information are expected to better predict clinical outcomes and capture important aspects of disease pathology [7].

5.2 RATIONALE FOR CURRENT STUDY

5.2.1. Mesenchymal stem/stromal cells (MSCs)

Mesenchymal stem/stromal cells (MSCs) are non-haematopoietic cells that reside in adult bone marrow and have the ability to self-renew and differentiate into tissues of mesodermal origin [8]. The relative ease by which MSCs can be expanded *ex-vivo* without significant manipulations has made them a potential candidate for use in regenerative medicine. They demonstrate extensive proliferative capacity *in vitro* and retain the ability to differentiate into several mesenchymal lineages, such as bone, cartilage, adipose tissue and muscle in lineage-specific cultures [9, 10]. Such multipotential capacity of MSCs appears to persist after transplantation - following intra-uterine injection of human MSCs into sheep, these cells engrafted and differentiated along multiple mesenchymal lineages (which was site-specific) and were still detectable for up to 13 months after transplantation [11]. *In vitro*, MSCs proliferate to spindle-shaped cells in confluent cultures. The cell yield after expansion varies with the age and condition of the donor and with the harvesting technique [12, 13]. In the absence of an agreed standardised marker, it is difficult to characterise MSCs so they are typically defined by a combination of phenotypic and functional characteristics. By flow cytometry, MSCs are negative for the haematopoietic markers CD14, CD34 and CD45. The cells remain positive for a number of adhesion molecules, including CD73, CD90, CD105 and CD166. The hallmark of MSCs is tri-lineage potential *in vitro*; i.e. the ability to differentiate into bone, cartilage and fat upon appropriate induction. MSCs give rise to the supportive stroma that constitutes the haematopoietic microenvironment and so sustain haematopoiesis *in vitro* by expression of a variety of haematopoietic cytokines (including IL-6, IL-11, leukemia inhibitory factor, stem cell factor and flt3/flk2 ligand) and growth factors but also via direct physical association [14, 15]. Human MSCs express human leukocyte antigen (HLA) class I and can be induced by interferon-gamma (IFNy) to express HLA class II which should allow recognition by alloreactive T cells. However, this does not happen suggesting that MSCs escape detection by the immune system. They have immunomodulatory effects demonstrated in co-culture experiments in which human MSCs (even after being pre-cultured with IFN- γ) fail to induce proliferation of allogeneic lymphocytes, as reviewed in [16]. MSCs also escape lysis by cytotoxic lymphocytes (CTLs) despite expression of HLA class 1, the usual targets for CTL lysis, and by Killer-cell Immunoglobulin-like Receptors (KIR) ligand-mismatched Natural Killer cells [17]. When MSCs are present in mixed lymphocyte cultures (MLC), T-cell proliferation is suppressed [18]. The suppression is independent of HLA and occurs when added MSCs are autologous to the stimulatory or responder lymphocytes, or derived from a third party donor. Lymphocyte proliferation induced by mitogens is also markedly reduced in the presence of autologous or allogeneic MSCs [18]. MSCs which have differentiated into adipocytes, osteoblasts and chondrocytes retain the capacity to reduce lymphocyte proliferation in MLC [19]. In fact, differentiation, particularly along the osteogenic lineage, enhances their immunosuppressive effect.

5.2.2. Preclinical work on MSCs as relevant to multiple sclerosis

Uccelli and colleagues have extensively evaluated the effect of MSCs on experimental autoimmune encephalomyelitis (EAE), an experimental model of MS. They demonstrated that MSCs infused intravenously homed to lymphoid organs, ameliorated EAE and reduced infiltration of the CNS by T cells, B cells and macrophages [20]. More recently the same group demonstrated that MSCs migrate into the inflamed CNS and whilst they do not differentiate into neural cells, this is still associated with reduced demyelination and axonal loss [21]. These results suggest that MSCs exert their therapeutic activity on the inflamed CNS through the peripheral control of immune cells and a protective effect *in situ* [22]. In addition, MSCs could foster endogenous repair through the recruitment of local neural precursor cells leading to some degree of endogenous neurogenesis and remyelination [23]. Many other features are also likely to be relevant for exploitation of MSCs in MS and CNS related diseases. MSCs display a potent antioxidant effect in EAE affected mice [24] and this neuroprotective effect may result from the release of anti-apoptotic molecules [25] and of neurotrophins [26]. These results support the concept that MSCs are likely to foster CNS repair not only by acting as tolerogenic cells, but also as bioactive providers of trophic and anti-apoptotic factors leading to neuroprotection [27]. Autologous bone marrow-derived MSCs from MS patients exhibit the same properties as MSCs from healthy donors in terms of proliferation, phenotype, *in vitro* differentiation and immunosuppressive ability [28, 29].

5.2.3. Clinical experience of MSC therapy in humans

Safety: It has been estimated that at least 2000 patients in total have been treated with MSCs either within the clinical trial setting or as anecdotal cases. This includes a number of patients with stroke and MS with no reports of significant graft related complications such as induction of immunodeficiency and its attendant complications of opportunistic infections and malignancy. The procedure is simple, relatively cheap, potentially widely applicable and the autologous source is ethically acceptable to all patients. Recent studies have shown that MSCs from autoimmune patients display normal ability to support haematopoiesis [30], immunomodulatory activity [31] and surface and molecular phenotype [32], thus supporting the possibility of safely utilising autologous MSCs for transplantation purposes in these patients.

Clinical experience in Graft-versus-host disease (GvHD) and Crohn's disease: Pre-clinical experiments have shown that MSC infusions can be highly efficacious in GvHD but ineffective if administered before the onset of the disease or after permanent tissue damage has occurred, thus indicating that an acute inflammatory microenvironment is crucial to promote the therapeutic properties of MSCs [33]. The initial clinical experience with GvHD supports such a notion, because MSCs have no effect on the chronic form of the disease. Pre-clinical studies have extensively supported this notion [34-36] and more recently, a European Blood and Marrow Transplantation (EBMT) multicentre clinical trial has described the successful use of MSCs in severe steroid-resistant acute graft-versus-host disease (GvHD), with 60% of patients obtaining complete durable remissions without toxicity [37]. MSCs are currently being tested for the treatment of Crohn's disease based on the observation that transplanted bone marrow cells can repopulate the human gastrointestinal tract and that BM-derived epithelial cells are remarkably increased during the epithelial regeneration after GvHD and ulcer formation [38].

Clinical experience of MSC treatment in MS: There are reports of small numbers of patients with MS who received IV or intrathecal (IT) infusions of MSC cells with some reported benefit. The results of an early phase I/II study of MSCs in neurological diseases reported on the administration of autologous MSCs to 19 amyotrophic lateral sclerosis and 15 MS patients [39]. MSCs were given as a combination of IT and IV injections, at doses up to $60-70 \times 10^6$ cells per injection per patient and patients were followed for 6–28 months with the main purpose being to determine feasibility and safety. No patient experienced significant side effects except that of mild meningeal irritation, having symptoms of headache and fever, in those receiving IT injections of cells. Magnetic

resonance imaging (MRI) in 20 of the patients did not reveal any unexpected pathology 1 year after MSC transplantation. No injection-related (early or late) infections were reported. Additional data on the use of MSCs in MS included a small study in 10 patients with MS from Iran, which reported no significant adverse events [40]. A MRC funded phase IIa study (with MS Society addendum funding) by the applicants ([name]) had also treated 10 patients. The importance of this latter study with regard to the current proposal is twofold: (1) it had established capability for cell expansion, validation, regulatory screening of autologous MSCs with successful intravenous delivery of autologous MSCs to 10 patients without any adverse events; and (2) the patients had progressive disease unlike the proposed study that is targeted at an “inflammatory-dominant” cohort with clinically and radiologically highly active disease. Thus we would regard the two studies as being complementary - with the MRC study providing significant added value, leverage and field-tested expertise and methodologies e.g. standard operating procedures (SOPs) to ensure that the desired outcomes are realistic. We are satisfied that sufficient information on the safety of autologous bone marrow-derived, intravenously administered MSCs exists to propose exploring such therapy in patients with active inflammatory MS. This position appears justified by the very latest publication which was a randomised, double-blind, placebo-controlled trial of autologous mesenchymal stem cells in multiple sclerosis [41]. A similar crossover trial design was employed and the results in 9 patients, whilst not powered to detect significance, showed a trend to lower mean cumulative number of GELs at 6 months in those patients treated with MSCs. No serious adverse events were identified.

5.2.4. Rationale for this study

Evidence from preclinical studies suggested that MSCs were an effective cell therapy for experimental autoimmune encephalomyelitis (EAE). In EAE, the IV injection of MSCs ameliorates the clinical course of acute disease and decreases demyelination, immune infiltrates and axonal loss, but has little or no effect in later stages of EAE. These results led to the conclusion that MSC administration should focus on individuals with on-going inflammation and before they develop irreversible disability. Pioneer small clinical studies in MS have already suggested their safety, thus paving the road from their clinical exploitation into larger phase II studies addressing their biological effect on markers of disease activity [39]. An international panel of MS neurology and stem cell experts, as well as immunologists formed an “International Mesenchymal Stem Cells Transplantation” (MSCT) Study Group with the aim to derive a consensus on the utilisation of MSCs for the treatment of MS along with protocols for the culture of the cells and the treatment of patients. This international consensus, based on the efforts of [name] (University of Genoa) and [name] (University of Ottawa), has been achieved and was published in 2010 [42]. In the consensus paper, the authors devised the synopsis of a phase I/II clinical trial, which will be fully adopted by scientists and clinicians belonging to the MSCT Study Group and presented to the respective national regulatory and funding agencies as single nation studies. This approach will enable the running of a series of parallel, independent but related, national studies adopting identical protocols, inclusion and exclusion criteria, primary and secondary outcomes collected on identical forms. The opportunity to pool the results of these studies will overcome the limitations of small phase I/II studies and provide enough statistical power to draw conclusions on the safety and efficacy of autologous MSCs transplantation in MS [42]. Our study will be conducted following the guidelines of the aforementioned consensus and utilise a protocol identical to the one adopted in other European countries and North America participating in this international collaborative effort. Identical, parallel but independent national trials will be conducted in Spain, Sweden, Denmark, France, Germany and Canada in order to assess the efficacy, safety and the toxicity of MSC infusion, as administered within this specific treatment protocol, in active MS. Evaluation of primary and secondary outcomes as well as exploratory outcomes will be carried out at the single national trial level but, more importantly, also on the entire data set obtained by pooling the results of all national trials, for an expected total of 160 randomised patients.

6. STUDY OBJECTIVES

6.1 PRIMARY STUDY OBJECTIVES

There are two co-primary objectives:

- To assess the safety of IV therapy with autologous MSCs in MS patients.
- To evaluate the activity of autologous MSCs in MS patients, quantified by the reduction in the number of new contrast-enhancing lesions (GEL) on MRI scans over a 24 week period.

6.2 SECONDARY STUDY OBJECTIVES

To gather preliminary information about the efficacy of the experimental treatment in terms of:

- combined MRI activity including MRI measures of remyelination
- clinical activity including incidence of relapses and disability progression and
- effect on immunological markers (for patients in the first phase of recruitment).

7. STUDY DESIGN

STREAMS is a randomised, double-blind crossover study comparing IV treatment with autologous MSCs vs. suspension media in MS patients with regards to the number of adverse events and new MRI activity (measured as GEL) at 24 weeks. A secondary analysis will compare the number of adverse events and GEL at weeks 0-23 and 24-48 within each treatment group (see Figure 1).

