- Pregnancy testing will be performed (if applicable).
- 80 ml blood research samples will be taken.*
- Urinalysis will be performed.
- EDSS, T25-FW, MSIS-29 and SF36 assessments will be carried out.
- An MRI will be carried out.

Week 16 ± 7 days

Patients will have the following performed:

- Concomitant medications will be recorded.
- Adverse events will be recorded.
- The patient will have their vital signs checked.
- 80 ml blood research samples will be taken.*

Week 20 ± 7 days

Patients will be admitted as a daycare and have the following performed:

- Concomitant medications will be recorded.
- Adverse events will be recorded.
- The patient will undergo a full physical examination including vital signs.
- Blood will be taken for haematological and clinical chemistry parameter measurement.
- Pregnancy testing will be performed (if applicable).
- Urinalysis will be performed.
- A lumbar puncture will be performed.
- 80 ml blood research samples will be taken.*

Week 24 ± 7 days

Subjects will have the following performed:

- An MRI will be carried out **prior to** infusion of the second study treatment.

Subjects will then be admitted as a day case to Hammersmith Hospital.

- Concomitant medications will be recorded.
- Adverse events will be recorded.
- The patient will undergo a full physical examination including vital signs.
- Blood will be taken for haematological and clinical chemistry parameter measurement.
- Pregnancy testing will be performed (if applicable).
- 80 ml blood research samples will be taken.*
- A Mantoux test will be performed.
- Urinalysis will be performed.
- EDSS, MSFC, MSIS-29 and SF36 assessments will be carried out.
- The study treatment will be infused.

Week 24 ± 7 days + 48/72 hours

Patients will have the following performed:

- Concomitant medications will be recorded.
- Adverse events will be recorded.
- The patient will have their vital signs checked.
- An EDSS assessment will be carried out.
- 80mls of blood research samples will be taken.*
- Reading of the Mantoux test.

Week 28 ± 7 days

Patients will have the following performed:

- Concomitant medications will be recorded.
- Adverse events will be recorded.
- The patient will undergo a full physical examination including vital signs.
- Blood will be taken for haematological and clinical chemistry parameter measurement.
- Pregnancy testing will be performed (if applicable).
- 80 ml blood research samples will be taken.*
- Urinalysis will be performed.

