12.8 MRI PROCEDURES

12.8.1. Outline

All patients will be scanned at one site: the MS Society-funded 3T MRI scanner at the UCL Institute of Neurology. Scans will be acquired at weeks 0, 4, 12, 24, 28, 36 and 48. If drop-out occurs before the study ends, all remaining MRI scans will be obtained, if possible, at the scheduled time-points or if this will not be possible, at an unscheduled visit (exit visit). The MRIs will be analysed by [name] group at the Institute of Neurology but as the data will also contribute to the international collaborative effort, these MRIs will be anonymised and sent to the Medical Image Analysis Centre (MIAC), located in Basel, Switzerland which is being used for analysis of the primary outcomes.

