12.8.4. Outcome measures

1. Cumulative number of new Gad-enhancing lesions weeks 4-24 inclusive (primary outcome measure to be analysed centrally by [name] group in Basel)
2. Cumulative number of new Gad-enhancing lesions weeks 28 to 48 inclusive
3. Cumulative number of persistent Gad-enhancing lesions weeks 4-24 and 28-48
4. Cumulative number of total Gad-enhancing lesions weeks 4-24 and 28-48
5. Volume of total Gad-enhancing lesions weeks 4-24 and 28-48
6. Cumulative number of new active lesions (new Gad-enhancing and new non-enhancing T2 lesions) weeks 4-24 and 28-48
7. Cumulative number of new and enlarging T2 lesions weeks 12 and 24 compared to baseline (week 0) and weeks 36 and 48 compared to week 24
8. Cumulative number of new T1 hypointense lesions on Gad-enhanced T1-weighted spin echo scans weeks 12 and 24 compared to baseline (week 0) and weeks 36 and 48 compared to week 24
9. Percentage brain volume change (PBVC) on 3D T1-weighted scans at weeks 12 and 24 compared to baseline (week 0) and weeks 36 and 48 compared to week 24
10. Regional atrophy changes in grey matter (using 3D T1-weighted scans and voxel based morphometry) and core white matter structural changes (using advanced diffusion analysis) at weeks 12 and 24 compared to baseline (week 0) and weeks 36 and 48 compared to week 24.
11. Serial analysis including all time points of magnetisation transfer ratio (MTR) measures of non-enhancing T2 lesions present at baseline (week 0)
12. Serial analysis including all time points of MTR measures of non-enhancing T1 hypointense lesions present at baseline (week 0)
13. Serial analysis including all time points of MTR measures of Gad-enhancing lesions present at baseline (week 0)
14. Serial analysis including all time points of MTR measures of new Gad-enhancing lesions that occur during the trial
15. Serial MTR measures at weeks 0, 12, 24, 36 and 48 of normal appearing grey matter
16. Serial MTR measures at weeks 0, 12, 24, 36 and 48 of normal appearing white matter

17. Serial analysis of diffusion-weighted imaging (DWI) data at all time points to assess axonal integrity and structural changes.

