13.3 EVALUATION OF PRIMARY OUTCOME VARIABLES

- Primary outcome: To assess the safety of intravenous therapy with autologous MSCs in MS patients. The safety of MSCs infusion will be evaluated including frequency, timing and severity of any adverse events in both MSCs and placebo treatment groups. A statistical comparison of the number of adverse events between treatment groups will be carried out using a chi-square test.
- Co-Primary outcome: To assess the activity of autologous MSCs in MS patients. The total number of gadolinium-enhancing lesions (GEL) at MRI at week 4, 12 and 24 will be compared between treatment groups using a Negative Binomial (NB) regression analysis, adjusting for the number of GEL at baseline.

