13.4 EVALUATION OF SECONDARY OUTCOME VARIABLES

Secondary outcomes: To gather preliminary information about the efficacy of the experimental treatment in terms of combined MRI activity, incidence of relapses and disability progression.

- The total number of GEL lesions at MRI at weeks 4, 12 and 24 in the group originally randomised to placebo will be compared with the number of GEL lesions at MRI at weeks 28, 36 and 48 following the infusion using a mixed effect generalised model with NB errors.
- The dependence on time of the total number of GEL at MRI will be analysed in the group originally randomised to active treatment using a mixed effect generalised model with NB errors.
- Combined unique MRI activity (new or enlarging T2, or enhancing or re-enhancing lesions). The total number of new or enlarging T2, or enhancing or re-enhancing lesions at MRI at week 4, 12 and 24 post-treatment will be recorded in the two groups using a Negative Binomial (NB) regression analysis with the treatment group as covariate.
- Number of relapses in MSCs treatment group vs. placebo group will be acquired and using a Negative Binomial (NB) regression analysis with treatment group as covariate
- Time to sustained progression of disability (RRMS group) will be analyzed with a Cox proportional-hazards model
- Proportion of progression-free patients in two groups will be compared with the use of a chi-square test (RRMS patients).
- Mean changes in Multiple Sclerosis Functional Composite (MSFC) score in MSC treatment group vs. placebo group compared to baseline will be analysed with a one-way ANOVA test.

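### Section 7 splits the within-group comparison at weeks 0-23 v 24-48, which conflicts with 7.1, 12.8.4 and 13.4 and, if followed, would count the pre-infusion week 24 scan in period 2

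*Combined protocol and SAP*

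**What the plan says.** Section 7 (Study design) sets out the within-group part of the crossover in one sentence: "A secondary analysis will compare the number of adverse events and GEL at weeks 0-23 and 24-48 within each treatment group". It names no statistical test.

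The MRI schedule is in 12.8.1: "Scans will be acquired at weeks 0, 4, 12, 24, 28, 36 and 48". The week 24 visit in 12.2.1 fixes the order of events on that day: "An MRI will be carried out prior to infusion of the second study treatment".

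The sections that define the GEL windows in detail use a different split:

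- 7.1 counts months 1, 3 and 6 for the primary endpoint and months 7, 9 and 12 for the period after crossover.
- 12.8.4 uses weeks 4 to 24 inclusive for the first period, and for the second: "Cumulative number of new Gad-enhancing lesions weeks 28 to 48 inclusive".
- 13.3 analyses the co-primary count "at MRI at week 4, 12 and 24 will be compared between treatment groups using a Negative Binomial (NB) regression analysis".
- 13.4 takes "The total number of GEL lesions at MRI at weeks 4, 12 and 24 in the group originally randomised to placebo", which "will be compared with the number of GEL lesions at MRI at weeks 28, 36 and 48 following the infusion".

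Two further secondary analyses state no weeks of their own: the dependence-on-time model for the active-first group in 13.4, and the paired analysis in 13.6.

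**The concern.** A scan taken before the second infusion can only reflect the first treatment. The section 7 split nevertheless puts it on the second-treatment side. It also leaves the two periods with different numbers of scans, so raw lesion totals would differ between periods even if nothing had changed. The document therefore gives two period definitions for the same GEL data, and only one is a like-for-like comparison.

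For adverse events there is no second definition to fall back on: 13.3 compares treatment groups and gives no within-group periods. Section 7 cuts at a nominal week, although the week 24 visit has a window of ±7 days and 8.4 delays the second infusion after a relapse treated with corticosteroids. Events near the changeover could then be charged to the wrong treatment.

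**Working it through.** **Inputs.** Scans at weeks 0, 4, 12, 24, 28, 36 and 48 (12.8.1). Week 24 scan before the second infusion (12.2.1). Mean 7.4 GEL, SD 11.4, over the three scans at weeks 4, 12 and 24; 50% decrease; 80% power; 5% significance level; 160 patients pooled; up to 23 in this trial (all 13.2). Assumed: two-sided test, 1:1 allocation (so 11 to 12 per sequence here), the same mean GEL at every scan, and totals not adjusted for scan count.

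**1. The plan's own figure.** Negative binomial shape k = 7.4² / (11.4² − 7.4) = 54.76 / 122.56 = 0.447. Patients per arm = (1.960 + 0.842)² × (1/7.4 + 1/3.7 + 2/0.447) / (ln 0.5)² = 79.75, so 80 per arm and 160 in total. The stated N is reproduced, and it already uses weeks 4, 12 and 24. The section 7 wording does not enter it.

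**2. Scans per window.** Mean per scan = 7.4 / 3 = 2.467.

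| Windows | Scans, period 1 v 2 | Expected GEL, no effect | Ratio, period 2 / period 1 |
|---|---|---|---|
| 13.4: 4, 12, 24 v 28, 36, 48 | 3 v 3 | 7.40 v 7.40 | 1.00 |
| Section 7, literal: 0, 4, 12 v 24, 28, 36, 48 | 3 v 4 | 7.40 v 9.87 | 1.33 |
| Section 7, week 0 dropped: 4, 12 v 24, 28, 36, 48 | 2 v 4 | 4.93 v 9.87 | 2.00 |

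**3. True 50% reduction, placebo-first group.** The week 24 scan still has the placebo rate; weeks 28, 36 and 48 have half of it.

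- 13.4 windows: (3 × 0.5) / 3 = 0.50.
- Section 7, literal: (1 + 3 × 0.5) / 3 = 0.83.
- Section 7, week 0 dropped: (1 + 3 × 0.5) / 2 = 1.25.

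Dividing by the number of scans removes the imbalance under no effect but not the misplaced scan: (2.5 / 4) / 1 = 0.63 instead of 0.50.

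**4. True 50% reduction, MSC-first group,** assuming full return to the placebo rate after crossover. 13.4-type windows: 3 / 1.5 = 2.00. Section 7, literal: (0.5 + 3) / (1 + 0.5 + 0.5) = 1.75. Week 0 dropped: 3.5 / 1 = 3.50.

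**5. Illustration with a test.** Section 7 names none. If a paired Wilcoxon test were applied to these windows (2,000 simulated trials, gamma-Poisson counts with k = 0.447, one patient effect shared by both periods), false positives at n = 11 would be about 5% for 3 v 3 scans, 32% for 3 v 4 and 76% for 2 v 4. These rates depend on the simulation model; the scan counts do not.

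**6. Adverse events.** If the second infusion takes place 7 days early, within the visit window, the first week after it falls in weeks 0-23 and counts against the first treatment. If it is late, or delayed under 8.4, events between week 24 and the actual infusion count against a treatment not yet given.

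**The case against.** The strongest reply is that section 7 is a short overview and the operative text is already right. Every passage that lists GEL scans puts week 24 in period 1, starting with 7.1, the next subsection. An analyst working from section 13 compares three scans with three and meets no problem. This stands, and it limits the point to a conflict of wording.

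A reader might infer more in three ways, and the documents do not support it:

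- **That the planned crossover analysis produces a false difference between periods.** It does so only if section 7 is taken to override 7.1, 12.8.4 and 13.4, and nothing says that it should.
- **That a real benefit would appear as harm** (1.25). This requires dropping the week 0 scan, whereas section 7 starts its window at week 0. On the literal reading the effect is diluted to 0.83, not reversed.
- **That the plan carries a false-positive rate of about 30% or 75%.** The Wilcoxon test appears only in 13.6, for the placebo-first group, with periods defined by treatment rather than by week. Under that definition a week 24 scan taken before the infusion belongs to the placebo period. Joining that test to the section 7 windows is a construction, useful only to show scale.

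The constant rate per scan is also an assumption. Patients are selected for a recent enhancing lesion (8.2, criterion 5), so week 0 in particular may differ from later scans.

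For adverse events a cut at week 24 is roughly right, because the second infusion is planned for then. What remains is that no other passage defines these periods, and that the infusion date can move.

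**Conclusion.** Wrong as written, and minor. Section 7 states a rule that gives a wrong answer if followed, and it contradicts 7.1, 12.8.4 and 13.4. With a constant GEL rate per scan and raw totals, the literal windows give a ratio of 1.33 with no effect and 0.83 for a true 50% reduction in the placebo-first group, against 1.00 and 0.50 with the 13.4 windows. Without the week 0 scan the figures are 2.0 and 1.25.

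The bias is conditional on section 7 being followed over 13.4. The co-primary comparison, its windows and the sample size of 160 are unaffected. The adverse-event part has no correct text elsewhere to rely on, but its size cannot be worked out from the documents, because it depends on how many second infusions move and on how many events fall near them.

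**What to change.** Rewrite the section 7 sentence so that GEL is compared at weeks 4, 12 and 24 against weeks 28, 36 and 48. State the same windows for the active-first time analysis in 13.4 and the paired analysis in 13.6, which now list none. For adverse events, define the periods by onset before or after the actual second infusion, using its recorded date and time, rather than by week number.

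This is essentially a one-sentence edit with two cross-references. It needs no new patients, visits, scans or data, and it removes a choice between conflicting windows once results are known.
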